2 BACKGROUND INFORMATION AND SCIENTIFIC RATIONALE

2.1 Background Information

Neonatal HSV is an uncommon disease that affects about 1500 infants yearly in the US (1-3) with recent studies indicating an increasing incidence over the last several years (4). Although uncommon, the disease can have devastating outcomes if not detected and treated early. The disease is divided into three classifications: skin, eye, and mouth (SEM), central nervous system (CNS), and disseminated. The classification is predictive of mortality and morbidity, with worse outcomes noted in the CNS and disseminated groups (5). SEM disease accounts for the majority of neonatal HSV disease cases (45%), followed by CNS disease (30%), and then disseminated disease (25%) (6).

Vidarabine was the first antiviral drug recommended for treatment of neonatal HSV disease in the 1970s. Although other antiviral agents were studied prior to vidarabine, they were not recommended for treatment of neonatal HSV disease as a result of their toxic side effects. Vidarabine was later replaced in the 1980s by acyclovir, an acyclic guanine analogue that inhibits viral replication by interfering with viral DNA polymerase (7-10). Although low dose acyclovir (30 mg/kg/day) was equally efficacious and demonstrated no reduction in mortality when compared to vidarabine (5, 6, 11), it was more favorable because of its less toxic profile and easier administration (6). A later study performed by the National Institute of Allergy and Infectious Diseases Collaborative Antiviral Study Group (CASG) evaluated intermediate dose acyclovir (45 mg/kg/day) and high dose acyclovir (60 mg/kg/day) to determine if outcome could be improved. High dose acyclovir demonstrated the greatest reduction in mortality rate from 14% in CNS disease and 54% in disseminated disease to 4% and 30% respectively (12). Thus, high dose acyclovir became the new standard of treatment for neonatal HSV disease, although the pharmacokinetics of high dose intravenous acyclovir dose were only assessed in two subjects (6, 12).

Currently the standard of care requires that infants diagnosed with neonatal HSV disease are treated with high dose intravenous acyclovir for 14-21 days depending on classification of the disease (6, 13); infants with SEM disease are recommended to receive 14 days of intravenous acyclovir whereas infants with CNS and disseminated disease are recommended to receive at least 21 days of intravenous therapy. Those with CNS disease could potentially require longer than 21 days of therapy as duration of therapy is determined on clearance of viral DNA from the CSF via repeat lumbar puncture performed near the end of the 21 days of therapy(14). If the viral DNA is still detected, intravenous acyclovir is continued for an additional week and another lumbar puncture is performed. Infants remain hospitalized for the entire duration of treatment in order to closely monitor for the potential risk of renal toxicity, a common reversible side effect of intravenous acyclovir. Once the infant has completed the treatment

course of intravenous acyclovir, they are transitioned to oral acyclovir (300 mg/m²/dose three times a day) and discharged home to complete a total of 6 months of suppressive therapy to prevent further neurologic injury by subclinical viral replication (13, 15). Suppressive therapy has significantly improved neurologic outcome (higher neurodevelopmental scores) in those infants with CNS disease and decreased the number of skin recurrences when started immediately after completion of treatment with IV acyclovir (15, 16).

Although vast advancements have been made in the treatment of neonatal HSV disease to reduce mortality and morbidity, there remains a high emotional burden and demand on families as a result of guilt, lengthy hospitalizations, and frequent administration of medications for a prolonged period of time. There is also a large financial burden on healthcare systems; the estimated costs for treatment of neonatal HSV disease accounting for admission and 6 months of follow up in a cohort of 900 infants from 2009-2015 was more than 60 million dollars (4), which will continue to increase as the incidence of the disease increases. Preventing neonatal HSV disease would be ideal to reduce the emotional stress and demand on families and financial burden on healthcare systems, but until that time, other means of reducing these stressors should be evaluated.

One way to potentially reduce the emotional stress and demands on families would be to decrease the length of hospital stay. Unfortunately, due to oral acyclovir's poor bioavailability of 15-30% (8-10, 17, 18), infant's require intravenous acyclovir for treatment in order to achieve the desired acyclovir plasma concentration. Valacyclovir, on the other hand, offers the possibility of use in infants for a portion of the treatment course as it can achieve similar concentrations to IV acyclovir because of its improved bioavailability of 50-54% (7, 8). Valacyclovir is an enteral prodrug of acyclovir synthesized by the addition of L-valine to acyclovir, and it is commonly used in the treatment and/or suppression of genital herpes in adolescents, adults, and pregnant women (9, 17, 19). Yet, only limited data exists on its use in children. One study performed by Kimberlin et al evaluated the pharmacokinetics of valacyclovir in children ranging from 1 month to 11 years of age. The study was able to recommend a valacyclovir dose of 20 mg/kg two to three times a day in children 3 months of age and older but was unable to recommend a dose for those younger than 3 months of age. This is because only one dose (25 mg/kg) was evaluated in those 1-2 months of age, and the 1-2 month old infants had a significantly higher AUC and C_{max} with a 25 mg/kg/dose of valacyclovir when compared to older infants due to decreased clearance (20). Thus, the pharmacokinetics of valacyclovir 20 mg/kg in infants less than 3 months of age needs to be evaluated in order to determine if valacyclovir can safely be recommended for use in the treatment of neonatal HSV disease. The dose recommended must approximate the plasma serum concentrations achieved with 20 mg/kg/dose of intravenous acyclovir.

UAB has contributed to and led many multi-center pharmacokinetic and pharmacodynamic studies including the study that evaluated the use of valacyclovir in children from 1 month to 11 years of age. Their experience will be extremely helpful in determining the PK data of valacyclovir and its potential use in the treatment course of neonatal HSV disease (specifically

with SEM disease). Due to biochemical properties, a liquid suspension of valacyclovir has not been produced, but the American Society of Health-System Pharmacists provides instructions on how to make an extemporaneously suspension that shows stability for at least 21 days (21).

2.2 Rationale

Valacyclovir is frequently used in adolescents and adults for the treatment and suppression of genital herpes; it is also recommended for use in pregnant women beginning around 36 weeks gestation with a history of genital herpes for suppressive therapy to decrease the risk of developing active lesions at time of delivery (19). In 2010, CASG performed a valacyclovir pharmacokinetic study in children one month to eleven years of age, and the study provided the first recommendations for valacyclovir dosing in children 3 months of age and older. The dose recommended was 20 mg/kg two to three times a day. Unfortunately, dosing recommendations could not be provided for those 1-2 months of age as only the 25 mg/kg dose was studied (20). Therefore, determining if 20 mg/kg every 8 hours is an appropriate dose of valacyclovir in infants less than 3 months of age is necessary before it can be recommended for use in the treatment of neonatal HSV disease. In order to determine if the dose is appropriate, pharmacokinetic data will need to be obtained for valacyclovir and compared to intravenous acyclovir pharmacokinetic data. Since pharmacokinetic data on intravenous high-dose acyclovir is limited to only two patients, this too will need to be evaluated for comparison purposes.

The proposed study is a PK study evaluating the pharmacokinetics of valacyclovir in infants 2-12 weeks of age. Only infants \leq 42 days of age who have been diagnosed with neonatal HSV disease on intravenous acyclovir per standard of care guidelines will be eligible for participation. The recommended dose of valacyclovir in children 3 months of age and older is 20 mg/kg two to three times a day, and thus, the dose to be studied will be 20 mg/kg/dose every 8 hours. Valacyclovir will be given anywhere from 2 days up to 7 days depending on when the pharmacokinetic data can be obtained. Data will only be obtained during weekday hours in the Child Health Research Unit (CHRU) at the University of Alabama at Birmingham. After pharmacokinetic data has been obtained, the infant will be switched to oral acyclovir per standard of care guidelines to complete 6 months of suppressive therapy. At the completion of the study, the pharmacokinetic data for valacyclovir 20 mg/kg every 8 hours in infants 2-12 weeks of age will be defined and will be evaluated to determine if the recommended dose is comparable to the currently recommended IV acyclovir dose. Results from this research will lay the foundation for future studies evaluating the use of valacyclovir in a portion of the treatment course for neonatal HSV disease - specifically SEM disease - to reduce the number of days an infant requires hospitalization and subsequently decrease the cost of admission. Additional studies will need to be performed to determine the CNS penetration of valacyclovir in order to determine its potential use in infants with CNS disease. All pharmacokinetic assays will be performed in the UAB Antiviral Pharmacology Laboratory, which has developed the methodology to process microspecimens of blood for several different drug concentration studies.

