Objectives:	
Primary:
 
• To define the pharmacokinetics of valacyclovir in neonates 2-12 weeks of age who are \geq 34 weeks gestation• To assess the safety of valacyclovir in treated infants 
Secondary:
 
• To assess the pharmacokinetics of high-dose parenteral acyclovir in neonates \geq 34 weeks gestation with virologically confirmed neonatal HSV disease who are receiving acyclovir as standard of care• To compare the pharmacokinetics of high-dose parenteral acyclovir to the pharmacokinetics of the proposed study dose of valacyclovir (20 mg/kg every 8 hours)

[figure not shown]
Outcome Measures	
Primary Endpoint:
 
 • Plasma pharmacokinetics parameters for valacyclovir AUC_8 • Cumulative incidence of Grade 3 or higher unsolicited adverse events, serious adverse events, or any adverse event that is not recovered / not resolved 
Secondary Endpoints:
 
 • Plasma pharmacokinetic parameters for parenteral acyclovir AUC_8 • Comparison of AUC_8 of 20 mg/kg IV acyclovir to the AUC_8 of 20 mg/kg PO valacyclovir

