2.3.2 Known Potential Benefits

Knowledge of the pharmacokinetic profile will aid in determining if 20 mg/kg/dose every 8 hours is the most appropriate dose of valacyclovir to be used in infants (≤ 84 days of age) for treatment of neonatal SEM HSV disease. It will also provide further baseline information for future studies to evaluate the use of valacyclovir in infants with neonatal HSV CNS disease. This information can aid in decreasing the length of hospitalization, emotional burden on families, and ultimately health care costs. Participants will not directly benefit themselves from participating, though.

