3 OBJECTIVES

3.1 Study Objectives

Primary:

- To define the pharmacokinetics of valacyclovir in neonates (\geq 34 weeks gestational age at birth and \geq 2000 g)
- To assess safety of valacyclovir administration

Secondary:

- To assess the pharmacokinetics of high-dose parenteral acyclovir in neonates \geq 34 weeks gestation with virologically confirmed neonatal HSV disease who are receiving acyclovir as standard of care
- To compare the pharmacokinetics of high-dose parenteral acyclovir to the pharmacokinetics of the proposed study dose of valacyclovir (20 mg/kg every 8 hours)

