Upon completion of the intravenous acyclovir per standard of care, the infant will be switched to valacyclovir 20 mg/kg every 8 hours for 2 and up to 7 days depending upon availability of the CHRU. The first dose of valacyclovir is to be given 8 hours after completion of the last dose of IV acyclovir. On day 2 (up to 7), the infant will return to UAB's CHRU for a PK profile to be obtained. The plasma specimens for the pharmacokinetic profile will be drawn at hour 0 (just prior to the scheduled valacyclovir dose and 8 hours after the last dose), at 1-2 hours after dose for a peak level, and 3-5 hours after dose. Once the infant completes the pharmacokinetic sampling, the infant will have completed the study and will be switched to oral acyclovir per standard of care guidelines to complete 6 months of oral suppressive therapy for neonatal HSV disease. The parent(s) or guardian will be instructed to have the infant follow with an infectious disease specialist for appropriate follow up of neonatal HSV disease while on suppressive therapy.

All participants will receive the standard of care treatment with 14 to 21 days of IV acyclovir (depending on disease classification) followed by 6 months of oral antiviral suppression. The only change is that the first few days of oral suppression will be with valacyclovir instead of acyclovir. Subjects with inadequate pharmacokinetic data for analysis (e.g., due to dropping out of the study before PK assessments are performed or blood sampling obtained but is

inadequate for analysis) may be replaced and will not count toward the total of 6 and up to 10 subjects.

Treatment Day 1 is the calendar day when the first dose of parenteral acyclovir was administered to the study subject for clinical purposes and will be the date against which follow-up visits will be defined. **Treatment Dose 1** corresponds to the first dose of parenteral acyclovir given to the study subject for clinical purposes. The study enrollment day is unlikely to be the same day as Treatment day 1 as individuals will need confirmation of neonatal HSV infection in order to be enrolled. Participants can enroll on or before treatment day 14. **Study Assessment Day 1** is the calendar day when the participant is enrolled in the study.

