5.1 Subject Inclusion Criteria

1. Signed informed consent from parent(s) or legal guardian(s)
2. Confirmation of HSV infection from surface culture/PCR, skin lesion culture/PCR, blood PCR, or CSF PCR (performed at UAB Virology lab)
3. \geq 34 weeks gestational age at birth
4. Weight at study enrollment is \geq 2000 grams
5. Receiving intravenous acyclovir, prescribed by the patient's physician for \leq 14 days
6. \leq 42 days of age at initiation of parenteral acyclovir
7. Creatinine \leq 1.2

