6 STUDY INTERVENTION/INVESTIGATIONAL PRODUCT

Although valacyclovir does not currently have a recommended dose for infants 2 months and younger, this study is mainly a pharmacokinetic sampling study of valacyclovir in infants 2 months and younger and is not being used for a therapeutic intervention. Currently intravenous acyclovir is recommended for treatment of neonatal HSV disease, which these infants will receive per standard of care guidelines. The infants will only receive a short course of valacyclovir (2 and up to 7 days) in order to obtain the pharmacokinetic profile and then will be switched to the standard of care oral acyclovir to complete 6 months of suppressive therapy. The only change is that the first few days of oral suppression will be with valacyclovir instead of acyclovir.

6.1 6.1. Study Product Description

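### Valacyclovir PK is claimed for ages 2-12 weeks, but on the scheduled IV course the oral profile comes no later than about 10 weeks of age (9 weeks for SEM disease)

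*Combined protocol and SAP*

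**What the plan says.** The target age is described in several places, and not in the same way.

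- **Protocol Summary, Objectives.** The first primary objective is "To define the pharmacokinetics of valacyclovir in neonates 2-12 weeks of age".
- **Section 2.2.** At the end of the study, "the pharmacokinetic data for valacyclovir 20 mg/kg every 8 hours in infants 2-12 weeks of age will be defined".
- **Section 2.3.2.** The profile is to help judge the dose of "valacyclovir to be used in infants (≤ 84 days of age) for treatment of neonatal SEM HSV disease".
- **Section 6.** The study is a "pharmacokinetic sampling study of valacyclovir in infants 2 months and younger".
- **Section 3.1.** The primary objective reads "To define the pharmacokinetics of valacyclovir in neonates" and then limits gestational age and weight. It gives no postnatal age range.

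The ages that can be sampled follow from other sections. Section 5.1 sets the upper limit at "42 days of age at initiation of parenteral acyclovir", and Section 4 and Section 5.2 agree. On IV duration, Section 4 states: "All participants will receive the standard of care treatment with 14 to 21 days of IV acyclovir (depending on disease classification". Section 2.1 says that "infants with SEM disease are recommended to receive 14 days of intravenous acyclovir". The period definitions in Section 4 and the schedule in Appendix A likewise use 14 days for SEM disease and 21 for CNS and disseminated disease. Valacyclovir follows 8 hours after IV acyclovir ends, and the oral profile is taken on day 2 to 7 of valacyclovir (Sections 4 and 7.3.3).

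**The concern.** The oldest age at which an infant can be sampled is fixed by the entry limit, the IV course and the sampling window. Added together on the scheduled course, these stop short of 12 weeks, yet Section 2.2 presents 12 weeks as something the study will establish. For SEM disease, the intended use named in Section 2.3.2, the shortfall is larger because the IV course is shorter.

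Age is not a neutral descriptor here. Section 2.1 reports that infants of 1-2 months had higher AUC and Cmax than older infants because of decreased clearance, and that no dose could be recommended below 3 months. It also notes that only one dose had been studied at 1-2 months; Section 2.2 gives that as the sole reason. On the protocol's own account, then, exposure changes with age in this range. A conclusion worded to 12 weeks would extend the result across ages with few or no observations, nearly up to the age at which the existing recommendation begins.

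**Working it through.** **Inputs**

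- Claimed range: 2-12 weeks = 14 to 84 days, a span of 84 − 14 = 70 days (Protocol Summary; Section 2.2)
- Age at IV start: 0 to 42 days (Section 5.1)
- Scheduled IV course: 14 days for SEM, 21 days for CNS and disseminated disease (Sections 2.1 and 4; Appendix A)
- Gap before valacyclovir: 8 hours, taken as 0 days (Section 4)
- Day of oral profile: 2 to 7 (Sections 4 and 7.3.3)
- IV extension: Section 2.1 makes 21 days a minimum for CNS and disseminated disease. It describes one further week in CNS disease if viral DNA persists, followed by re-testing, and states no maximum.

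**Formula.** Age at oral profile = age at IV start + IV days + valacyclovir day.

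**Trying to reproduce 84 days.** At the latest start and latest profile, 84 = 42 + IV days + 7, so IV days = 35. The schedule gives 14 or 21. With 21 IV days, reaching 84 would need a start at 84 − 21 − 7 = 56 days of age, which is outside eligibility. The stated upper limit does not reproduce from the schedule.

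**Ages that can be reached**

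| IV course | Earliest | Latest |
|---|---|---|
| SEM, 14 days | 0 + 14 + 2 = 16 d | 42 + 14 + 7 = 63 d (9 weeks) |
| CNS or disseminated, 21 days | 0 + 21 + 2 = 23 d | 42 + 21 + 7 = 70 d (10 weeks) |
| CNS, one extra week (28 days) | 0 + 28 + 2 = 30 d | 42 + 28 + 7 = 77 d (11 weeks) |
| CNS, two extra weeks (35 days; assumed) | 0 + 35 + 2 = 37 d | 42 + 35 + 7 = 84 d (12 weeks) |

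Counting calendar days instead of elapsed days lowers each figure by one (69 days overall and 62 for SEM on the scheduled course).

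**Size of the gap at the upper end**

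- All infants, scheduled course: (84 − 70)/70 = 14/70 = 20%
- SEM: (84 − 63)/70 = 21/70 = 30%

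**Lower end.** The earliest profile, at 16 days, agrees with 2 weeks closely enough, and dosing can begin at about 14 days.

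**Participation limit.** The Protocol Summary gives participation of up to 26 days. With two extra IV weeks and a day-7 profile, sampling falls on treatment day 35 + 7 = 42, which is 42 − 14 = 28 days after the latest permitted enrolment (treatment day 14). That exceeds 26. This is supporting evidence only, because the 26-day figure also fails for a standard CNS course enrolled on treatment day 1 (21 + 7 = 28).

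**The case against.** The strongest reply is that 21 IV days is a floor, not a ceiling. Section 2.1 allows CNS treatment to continue, no section excludes such infants, and 42 + 35 + 7 gives exactly 84. This stands in part. A reader might infer that ages above 70 days can never be observed; the documents do not support that. They support only that such ages need IV treatment past 21 days together with a late start, and that 84 days needs two extra weeks, a start at the 42-day limit and sampling on day 7.

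Second, SEM dosing need not rest on SEM infants alone: all three disease classes are enrolled, and Section 11.4 plans no analysis by class. An SEM course begun by day 42 also ends by 42 + 14 = 56 days, inside the sampled range. This tempers the practical consequence for SEM. It does not supply data for the 84-day limit that Section 2.3.2 states.

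Third, the range carries no statistical weight. Section 3.1, the endpoints, the hypothesis, the sample size and the analysis plan do not use it. That is correct, and it makes this a matter of the stated target population and conclusion, not of a faulty analysis.

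Fourth, the wording in Section 6 may not conflict at all. Sections 2.1 and 2.2 treat 1-2 months and 3 months and older as adjoining groups, so two months and under could mean anything below 3 months. Read strictly, it would leave out infants the schedule produces, for example 42 + 21 + 2 = 65 days. The phrase is ambiguous.

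**Conclusion.** The point holds for the scheduled course. The latest age at the oral profile is 70 days, or 63 days for SEM disease, against 84 claimed. The uncovered part is the last 14 of 70 days (20%), or 21 of 70 (30%) for SEM. Ages 71-84 days depend on extended IV treatment; with 6 to 10 infants in total, that does not justify a statement that PK in the range will be defined.

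This rests on IV courses of 14 or 21 days, no gap before valacyclovir, and elapsed-day counting. The second extra week is an assumption, since Section 2.1 gives no count.

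Three stronger readings are not supported:

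- A reader might see three competing upper limits. Twelve weeks and 84 days are the same limit, and the Section 6 phrase is ambiguous.
- A reader might say the formal primary objective makes the 2-12 week claim. Only the summary's version does; Section 3.1 gives no range.
- A reader might put the gap at 16/70 = 23% (23/70 = 33% for SEM) by adding the two days from 14 to 16. The lower end is not a real shortfall.

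**What to change.** Use one age statement in the Protocol Summary objective and in Sections 2.2, 2.3.2, 3.1 and 6: about 2 to 10 weeks of postnatal age at the oral profile, older only after extended IV treatment. Word the conclusion so that it covers the ages actually sampled. In Section 11.4, add a listing or plot of each infant's AUC8 against postnatal age at the profile.

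The data are already collected: date of birth under Section 7.2.1, and dose dates and sampling times under Sections 7.3.3 and 8.2.1.1. The cost is a wording amendment, one extra display and a slightly narrower claim. Nothing here implies a change to eligibility, dose, treatment duration, sampling or sample size.
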